Baseline Measure Information *

A group of demographic characteristics will be measured in the study, including gender, age, marital status, income per month, gender of lost kid, length of lost kid.

Baseline Measure Title *

- Age * : Continuous(years)
- Gender * : Female, Male
- Marital status: with a spouse, without a spouse
- Income per month: Categorical:
 - <=1000 RMB
 - >1000 and <2000 RMB
 - >=2000 RMB
- Gender of lost kid: Female, Male
- Length of lost kid: Continuous(years)

Measure Type *

- Count of Participants: Gender, Marital status
- Mean: Age, Length of lost kid
- Number: Gender of lost kid, Income per month

Measure of Dispersion *

- Standard Deviation
- Inter-Quartile Range
- Full Range

Baseline Measure Data *

The value(s) for each baseline measure, for each group and overall cannot obtain right now since the study has not been started.

3. Outcome Measures

Outcome Measure Information *

A questionnaire will be used during each measurement, including several scales in it. The saliva test of Dehydroepiandrosterone will also be done in each measurement.

Outcome Measure Type *

- Primary

Outcome Measure Title *

- Psychological resilience: a kind of ability to bounce back from adversity measured by Connor-Davidson Resilience Scale (CD-RISC). It is a self-reported scale by adding up 25 items and the total score ranges from 0-100, with higher score reflects higher resilience. The differences within two times frame are the changes of psychological resilience
- Depression: depressive mood in recent two weeks measured by Zung Self-rated Depression Scale (SDS). It is a self-reported scale by adding up 20 items and the total score ranges from 20-80, with higher score reflects higher depression. The differences within time frames are changes of depression
- Subjective well-being: a feeling of happiness measured by Campbell Index of well-being (IWB). It is a self-reported scale by adding up 8 items and the total score ranges from 2.1-14.7, with higher score reflects higher subjective well-being. The differences within time frames are change of subjective well-being
- Social avoidance: the phenomenon that a person is absent from normal social interaction with others measured by Social Avoidance and Distress Scale(SAD). It is a self-reported scale by adding up 14 items and the total score ranges from 0-14, with higher score reflects social avoidance. The differences within time frames are the changes of social avoidance

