- Sleeping quality: a reflection of one's mood in recent month measured by Pittsburgh sleep quality index(PSQI). It is a self-reported scale, with total score higher than 19 reflects sleeping disorder. The differences within each time frames are the changes of sleeping quality
- Post traumatic growth: the positive growth after an adversity measured by Post Traumatic Growth Inventory(PTGI). It is a self-reported scale by adding up 24 items and the total score ranges from 0-120, with higher score reflects more growth. The differences within time frames are changes of post-traumatic growth
- Health care behavior: a person's self-care behavior measured by Health Promoting Lifestyle Profile-II(HPLP-II). It is a self-reported scale by adding up 40 items in four dimensions. The total score ranges from 40-160, with higher score reflects better health care behavior. The differences within time frames are changes of health care behavior
- Concentration of dehydroepiandrosterone in saliva: a kind of hormone that reflects the person's psychological stress collected by Sarstedt saliva collection tube by chewing the sterile cotton strips for 60 seconds. It will be tested by enzyme-linked immunosorbent assay (ELISA) with Kit Number of HT81012 and Origin site in Canada PLLabs

Outcome Measure unit *

The psychological resilience, depression, subjective well-being, social avoidance, sleeping quality, post traumatic growth, and health care behavior are measured by scales with no unit.

Dehydroepiandrosterone has its concentration unit of pg/ml.

Outcome Measure Time Frame *

There will be four measurements, before the intervention, immediately after intervention, 3-month after intervention, and 12-month after intervention. They are defined as T0, T1, T2, T3 respectively.

Analysis Population Information

Overall Number of Participants Analyzed *

There will be 150 participants totally enrolled in the study.

Outcome Measure Data Table

Measure Type *

- Mean

Measure of Dispersion/Precision *

- Standard Deviation

Outcome Data *

The measurement value(s) for each outcome measure cannot obtain right now since the study has not been started.

Statistical Analysis Overview

Comparison Group Selection [*]

We will compare three groups' data.

Type of Statistical Test [*]

- Superiority
- Other (descriptive analysis)

P-Value [*]

P-Value will be set at 0.05.

Method [*]

- ANOVA
- Chi-Squared
- t-Test, 2-Sided

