- Other: repeated measurement of variance analysis within different measurements among different groups

Estimation Parameter [*]

- Mean Difference (Final Values)

4. Adverse Event Information

Time Frame *§

The intervention lasts 8 weeks, and we will record the adverse event each week. Then we will do follow-up immediately after intervention, 3-month after intervention, and 12-month after intervention. we will record the adverse event at each follow-up.

Adverse Event Reporting Description [*]

We will add relevant information about adverse event after finishing the study.

Collection Approach for Table Default *§

- Systematic Assessment: The psychotherapist will routinely determine whether or not certain adverse events have occurred through regular investigator assessment during intervention and in each follow-up.
- Non-Systematic Assessment: Self-reporting by participants or occasional assessment by the psychotherapist.

Adverse Event Term *

The most possible adverse event may be the psychological discomfort because the participants are experiencing bereavement.

We will provide information for in three tables summarizing adverse events in each group, including all-cause mortality, serious adverse events, and other (not including serious) adverse events.

Organ System *

- Psychiatric Disorders

5. Limitations and Caveats

There may be several limitations.

We may not reach the target number of participants because the bereaved parents present social avoidance and may not interested in the intervention. We will invite social worker to help recruiting and make calls to all registered bereaved parents.

The measurements are mostly based on self-reported scales and may lead to unreliable data. We will give instruction before fulfilling the questionnaire to ensure the participants understood.

6. Certain Agreements

Are all PIs Employees of Sponsor? *

- No: The principal investigator is not an employee of the sponsor

There is no agreement between the agent(university) and the principal investigators. The principal investigators are graduate students in the university. The principal investigators (PIs) can discuss the results of the study at a scientific meeting or any other public or private forum, or to publish in a scientific or academic journal information concerning the results of the study.

7. Results Point of Contact

Name or Official Title *

Professor: [name]

Position title: Director of Nursing Psychology Research Center

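### Individual worsening on the SDS, which is close to the named likely harm, is not tabulated with the adverse events

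*Combined protocol and SAP*

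**What the plan says.** **Expected harm.** Section 4 (Adverse Event Term) states: "The most possible adverse event may be the psychological discomfort because the participants are experiencing bereavement". The only organ system listed is psychiatric.

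**How harms are collected.** Section 4 (Time Frame) has adverse events recorded weekly through the 8-week intervention and again at each follow-up. Under Collection Approach there are two routes. The systematic route is a regular determination by the psychotherapist, during the intervention and at each follow-up, of events that the plan does not specify. The other is "Non-Systematic Assessment: Self-reporting by participants or occasional assessment by the psychotherapist". Results go into three tables by group: deaths from any cause, serious events and other events.

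**What is measured.** Section 3 (Outcome Measure Title) lists the SDS as a primary outcome: "It is a self-reported scale by adding up 20 items and the total score ranges from 20-80, with higher score reflects higher depression". Change is defined only in general terms: "The differences within time frames are changes of depression". On timing: "There will be four measurements, before the intervention, immediately after intervention, 3-month after intervention, and 12-month after intervention". On arms: "We will compare three groups' data".

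**How the SDS is analysed.** Section 3 gives mean and standard deviation, a mean difference in final values, and ANOVA, t-test and repeated-measures analysis of variance. Chi-squared and descriptive analysis are also listed, but neither is attached to any SDS category. The only stated use of chi-squared is for baseline counts (section 2, Arm/Group Information).

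**Contact with Group C.** Section 1 (Arm/Group Description) describes Group C as receiving routine service from social workers. No psychotherapist is mentioned for that arm.

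**The concern.** The trial holds a standardised measure close to the harm it expects, taken on one schedule in every arm, and does not use it when harms are reported. Two things follow.

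First, the specified SDS analyses compare group averages. If some participants deteriorate while most improve, the average can still look favourable, and no planned SDS summary would show how many got worse.

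Second, the planned harm counts depend on judgement about undefined events and on what participants volunteer. If participants in Groups A and B are seen more closely than those in Group C, the adverse-event tables would compare arms with unequal ascertainment. An SDS-based count would not depend on the psychotherapist.

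**Working it through.** The plan states no figure on this point, so there is none to reproduce. The check has three parts.

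**1. Is there a link from an individual SDS rise to a harm count?** Set side by side, section 3 defines SDS change and analyses it through means, while section 4 defines adverse events through assessment and self-report. Neither gives an SDS margin, a count of participants who deteriorate, or a cross-reference to the other. There is no link.

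**2. Can the mean hide a worsening subgroup?** Let a fraction w of an arm worsen by 1 SD and the rest improve by g SD. Mean improvement is (1 - w) × g - w × 1. Setting this to an assumed 0.5 SD gives g = (0.5 + w) / (1 - w). With 50 per arm (section 1):

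| w | Participants worsening by 1 SD | g needed in the others | Check |
|---|---|---|---|
| 10% | 5 | 0.6/0.9 = 0.667 SD | (45 × 0.667 - 5)/50 = 0.5 |
| 20% | 10 | 0.7/0.8 = 0.875 SD | (40 × 0.875 - 10)/50 = 0.5 |
| 30% | 15 | 0.8/0.7 = 1.143 SD | (35 × 1.143 - 15)/50 = 0.5 |

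The same mean improvement is compatible with 5, 10 or 15 participants worsening by a full SD. The values of w and the 0.5 SD improvement are assumptions.

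**3. What could a by-arm count show with 50 per arm?** Worsening rates are also assumed. For a two-sided 0.05 test of two proportions:

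| Rates compared | Power |
|---|---|
| 5% v 15% | 38% |
| 5% v 20% | 62% |
| 5% v 25% | 81% |
| 10% v 20% | 29% |
| 10% v 30% | 71% |

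For 10% v 20%, the standard error of the risk difference is √(0.1 × 0.9/50 + 0.2 × 0.8/50) = √0.005 = 0.071. The 95% interval is therefore about 10 ± 13.9 percentage points. If none of 50 worsened, the upper two-sided 95% limit is 1 - 0.025^(1/50) = 7.1%. The count is useful as description with intervals, not as a test.

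**The case against.** The strongest reply is that section 4 already provides for individual harms. A reader might infer that individual worsening is never counted, and the documents do not support that. Assessment is scheduled weekly and at each follow-up, participants may report for themselves, and events are tabulated by group. A participant in distress can reach those tables. What is absent is narrower: worsening as defined by the SDS.

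A reader might also infer that the sessions make participants dwell on their loss and so are likely to cause harm. The themes in section 1 (Arm/Group Description) do not say so.

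Nor does a simple normal model demonstrate hidden harm. Assume a mean improvement of 3 points and an SD of change of 6, 10 or 14. The proportion rising by 5 points or more is P(Z ≥ 8/SD) = 9%, 21% or 28%. An arm with no mean change gives P(Z ≥ 5/SD) = 20%, 31% or 36%, which is more. Under that model the proportion is fixed by the mean and SD of change, so it reflects ordinary variability. Masking requires heterogeneous response, which is possible but not shown.

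Further limits stand. Any margin is conventional. The SDS covers depressive mood over two weeks and is not taken during the weekly sessions. A rise at T3 need not reflect treatment. Participants are told their group (section 2, Arm/Group Description), so the SDS avoids dependence on the psychotherapist but not on knowledge of allocation. These limits make the table descriptive and make the comparison with Group C essential. They do not remove the gap.

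**Conclusion.** The point holds in a limited form. The plan names psychological discomfort as its likeliest harm and collects the SDS on one schedule in all arms, but does not tabulate SDS-defined individual worsening with the harms. Its size cannot be estimated from the documents, which give no SDS standard deviation, expected change or worsening rate. The 20% example shows what a mean could conceal if response is heterogeneous, not what is expected here.

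Unequal ascertainment between arms is an inference. It rests on the plan naming the psychotherapist as systematic assessor and only social workers for Group C, without saying who assesses Group C. The documents do not establish that harms in Group C would be missed.

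This is an inexpensive improvement to harm reporting that should be made. It does not invalidate the planned analyses.

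**What to change.** Add one descriptive table to section 4, beside the adverse-event tables. By arm, at T1, T2 and T3, give the number and percentage of participants whose SDS rose from their own T0 score by at least a set margin. The denominator should be those with an SDS score at T0 and at that visit. Add risk differences for Group A v Group C and Group B v Group C, with 95% intervals.

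The investigators should fix and justify the margin before outcome data are analysed. One example is 0.5 of the pooled T0 SD, with 1 SD as a sensitivity analysis. State that the table is descriptive.

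The cost is one table from data already collected, with no extra visit or instrument. The downsides are that the margin is conventional and that some rises will be measurement noise, for which Group C shows the background rate. With about 50 per arm the intervals will be wide, so a lack of difference must not be read as evidence of no harm.
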